#### 9.1.3.4. As Treated Population

All randomized subjects, analyzed according to the actual treatment received. Subjects randomized to RDN who do not get treated will be analyzed in the control arm. Subjects who meet the anti-hypertensive medication escape criteria (OSBP>180 mmHg or safety reasons) will be analyzed using Last Observation Carried Forward (LOCF) for their blood pressure measurements out to 3 months. Office and ambulatory blood pressure outcomes out to 3 months will be presented for this population.

#### 9.1.4. Crossover Procedures

Control subjects may crossover and receive renal denervation therapy at or after their 6 month follow-up visit. For the subjects who had already completed their 6 month visit, the decision to crossover must take place at their next in person visit. All subjects will have 30 days from the Crossover visit (6, 12, 24, 36 month follow-up or Unscheduled visit) to undergo the crossover procedure. Subjects who are more than 30 days from their 6, 12, 24 or 36 month, must complete a crossover Baseline visit prior to crossing over. Control subjects who are coming in for their scheduled 6, 12, 24 and 36 month follow-up visit do not need to come in for a crossover Baseline visit if all the required crossover Baseline procedures occurred, including lipid panel, hs-crp and uric acid blood tests. To crossover, the subject cannot meet any of the anatomical and glomerular filtration rate (eGFR) exclusion criteria, and cannot be pregnant, nursing or planning to become pregnant during the course of the study follow-up. Crossover subjects will undergo follow-up visits at 1, 3, and 6 months ( $\pm$  14 days) and annually at 12 and 24 months ( $\pm$  30 days) post-procedure.

# 9.2. General Methodology

Descriptive statistics of continuous outcomes will be presented by treatment group and include sample size, mean, median, standard deviation, minimum and maximum. For categorical outcomes, the number and percentage of subjects in each category will be presented by treatment group. Statistical

comparisons between treatment groups will be made using the independent samples t-test for continuous outcomes and Fisher's exact test for categorical outcomes. Paired tests will be used to compare changes from baseline to follow-up within each treatment group. All statistical analyses will be performed using SAS for Windows (version 9.2 or higher) or other widely accepted statistical or graphical software. Patient data listings and tabular and graphical presentations of results will be provided. Unless otherwise specified, a two-sided 0.05 level of significance will be used to declare treatment groups significantly different.

## 9.3. Poolability Analyses

#### 9.3.1. Poolability of study centers

The following analyses will be performed to evaluate the poolability of data from different study centers. If the resulting tests are significant at the 0.15 level, further exploratory analysis will be attempted to identify covariates that may explain differences. Otherwise, the data will be considered to be poolable across study centers.

- A logistic regression will be conducted, with Major Adverse Events (MAE) as the dependent variable, and treatment, study center, treatment \* study centers as independent variables. If the interaction term is not significant at 0.15 level, then the treatment effect in the primary safety endpoint is considered consistent among the sites.
- A linear regression will be conducted, with change in systolic blood pressure from baseline to 3
  months as measured by 24-hour systolic Ambulatory Blood Pressure Monitoring (ABPM) as the
  dependent variable, and baseline systolic ABPM, treatment, study center, treatment \* study
  center as independent variables. If the interaction term is not significant at 0.15 level, then the
  treatment effect in the primary effectiveness endpoint is considered consistent among the study
  centers.

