**SPYRAL Pivotal - SPYRAL HTN-OFF MED First Interim Analysis**

The SPYRAL PIVOTAL - SPYRAL HTN-OFF MED study is a multi-center, international, prospective, single blinded, randomized, interventional, sham-controlled study. In order to test the hypothesis that renal denervation decreases blood pressure and is safe when studied in the absence of antihypertensive medications, study subjects will be randomized to the Denervation or Control group in a 1:1 fashion. In addition to subjects being blinded to their randomization assignment, site personnel involved in the measurement of office blood pressure will also be blinded to study subjects’ randomization assignment through the primary endpoint to prevent potential bias of results. Subjects will be studied in the absence of antihypertensive medications to assess the impact of renal denervation on systolic blood pressure in the absence of medication.

Study enrollment was stopped for efficacy after the first interim analysis in February 2020. Data from the initial 80 patients with 3 months follow up from the SPYRAL HTN-OFF MED study was combined with data from the initial 251 patients with 3 months follow up from the

[figure not shown]
SPYRAL PIVOTAL-SPYRAL HTN-OFF MED study and was presented at ACC World Congress of Cardiology in March 2020. Concurrently, an article presenting the data was published in the Lancet. A brief summary of the SPYRAL PIVOTAL-SPYRAL HTN-OFF MED data is provided below.

The primary endpoint, change in 24-h blood pressure at 3 months, was compared between groups. Drug surveillance was done to ensure patient compliance with absence of antihypertensive medication. The primary analysis was done in the intention-to-treat population. Safety events were assessed to 3 months.

From June 25, 2015, to Oct 15, 2019, 1519 patients were enrolled, of whom 1188 were excluded because they did not meet inclusion criteria. 166 were randomly assigned to renal denervation and 165 to the sham procedure (80 were included in the pilot and 251 in Pivotal).

There were no major safety events reported at 1 month. There was one major safety event in each treatment group up to 3 months (one admission to hospital for hypertensive crisis or emergency in the renal denervation group and one new stroke in the sham procedure group), and neither was attributed to the device or trial procedures.

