### 9.3.3. Poolability of North America (US and Canada)/Rest of World (ROW)

The following analyses will be performed to evaluate the poolability of data from North America (NA) and Rest of World (ROW) sites. If the resulting tests are significant at the 0.15 level, further exploratory analysis will be attempted to identify covariates that may explain differences. Otherwise, the data will be considered to be poolable across regions.

- A logistic regression will be conducted, with MAE as the dependent variable, and treatment, NA/ROW, treatment \* NA/ROW as independent variables. If the interaction term is not significant at 0.15 level, then the treatment effect in the primary safety endpoint is considered consistent between NA and ROW subgroups.
- A linear regression will be conducted, with change in systolic blood pressure from baseline to 3
  months as measured by 24-hour systolic Ambulatory Blood Pressure Monitoring (ABPM) as the
  dependent variable, and baseline systolic ABPM, treatment, NA/ROW, treatment \* NA/ROW as
  independent variables. If the interaction term is not significant at 0.15 level, then the treatment
  effect in the primary effectiveness endpoint is considered consistent between NA and ROW
  subgroups.

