#### 9.9.1.1. Primary Safety Endpoint Analysis

Medtronic is using a performance goal approach to power the primary safety endpoint.

The safety performance goal for the Major Adverse Event (MAE) rate was developed based on review of and comparison to event rates of other renal interventions. The review of renal intervention literature reported event rates of 3.6 to 17.2%. The reported events differed among the studies; however, for a subset of these studies, we could estimate rates for a composite of events similar to our protocol's MAE composite (see Table 1 below). The major adverse event rate from these studies was 7.1%.

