The performance goal is set to be 7.1%, which is the meta-analysis rate from historical trials in Table 1. The primary safety null and alternative hypotheses are:

 $H_0$ :  $\pi$  ≥ 7.1% vs.

 $H_a$ :  $\pi < 7.1\%$ 

where  $\pi$  is the MAE rate for patients undergoing renal denervation. Under the assumption that the true rate is 3.5%, and using a one-sided 0.05 level of significance, an evaluable sample size of 253 renal denervation patients yields 80% power to reject the null hypothesis in favor of the alternative. The exact binomial test was used for the sample size calculation for the primary safety endpoint hypothesis.

In other words, the primary safety endpoint hypotheses is designed to show whether the true MAE rate is lower than 7.1%. Compared to the literature reported event rates for renal intervention, we believe that these thresholds are appropriate for demonstrating safety of the device given the expected performance rates of similar renal intervention trials, particularly when balanced with the expected blood pressure reductions.

Medtronic proposes multiple sources of study patients as shown in Table 2 below to ensure 253 patients treated with the Symplicity Spyral catheter (including branch treatment) are available for analysis. The first 253 subjects with evaluable safety data from the sources in Table 2 will be used to perform the primary safety endpoint analysis.

With a sample size of 253 and a one-sided significance level of 0.05, a maximum of 11 subjects with MAE will enable us to meet the safety primary endpoint, resulting in an event rate of 4.3% with a one-sided 95% upper confidence bound of 7.09% using the exact binomial method.

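### The treatment-by-centre MAE model in SAP 9.3.1 cannot be estimated at about 50 centres, and the MAE poolability rules in 9.3.1 to 9.3.3 do not test the primary safety endpoint, so non-significance should not be read as consistency

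*SAP*

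**What the plan says.** SAP 9.3.1 states: "A logistic regression will be conducted, with Major Adverse Events (MAE) as the dependent variable". The predictors are treatment, study centre and their product. If the interaction is not significant at 0.15, "then the treatment effect in the primary safety endpoint is considered consistent among the sites", and the section then takes the data as poolable across centres. A significant result leads only to exploratory work on covariates. SAP 9.3.2 (US against Canada) and 9.3.3 (North America against rest of world) have the same form with a two-level region in place of centre; 9.3.3 reads "A logistic regression will be conducted, with MAE as the dependent variable".

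SAP 9.9.1.1 defines the endpoint these rules refer to: "Medtronic is using a performance goal approach to power the primary safety endpoint". The parameter "is the MAE rate for patients undergoing renal denervation", and it is tested against a fixed value: "The performance goal is set to be 7.1"%. The design assumes a true rate of 3.5% and 253 denervated subjects, and "a maximum of 11 subjects with MAE will enable us to meet the safety primary endpoint". Those 253 may come from OFF MED, ON MED and crossover subjects (SAP Table 2).

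SAP 6 allows up to 50 centres and up to 433 randomised subjects, and SAP 7 randomises 1:1 within centre. SAP 9.3 does not name the test statistic, the degrees of freedom or the analysis set. It has no rule for combining small centres and no fallback for sparse events or non-convergence.

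**The concern.** There are two separate problems. First, a saturated centre-by-arm model is fitted to a rare event, and failure to reject is then treated as a positive finding. If the test has almost no chance of rejecting at the planned number of centres, the finding carries no information about whether safety varies between centres. Second, the interaction measures whether the difference between denervation and sham varies by centre or region. The primary safety hypothesis has no sham term. What pooling requires is that the denervation-arm MAE rate is similar across the groups being pooled, and none of the three MAE models tests that.

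At stake is a pre-specified statement of homogeneity on the primary safety endpoint, in a trial whose data are intended for regulatory submissions (Protocol C.1), that the analysis cannot support.

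**Working it through.** **1. The plan's own safety figures reproduce.** Exact one-sided binomial with n = 253, null rate 7.1% and cut-off 11: P(X ≤ 11 | 7.1%) = 0.0496 and P(X ≤ 11 | 3.5%) = 0.820. The exact one-sided 95% upper bound for 11/253 is 7.09%. The smallest n with at least 80% power is 253. The safety sizing is not in question.

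**2. Expected events.** In the safety set: 253 × 0.035 = 8.9. In the randomised denervation arm at full size: 433/2 × 0.035 = 7.6. The model has a treatment term, so it needs both randomised arms and control events also enter. The documents give no control-arm MAE rate, so I take 0% to 7.1% as an assumed range.

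**3. Size of the model.** For 50 centres: intercept 1 + treatment 1 + centre 49 + interaction 49 = 100 parameters, with 49 interaction degrees of freedom. Average cell size is 433/100 = 4.3 subjects.

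**4. Finite estimates.** The model is saturated in centre by arm, so every one of the 100 cells needs at least one event and one non-event. That takes at least 100 MAEs. At 3.5% in both arms, 433 × 0.035 = 15.2 are expected. The chance that every cell holds an event is (1 − 0.965^4.33)^100 ≈ 3 × 10⁻⁸⁵. With 21 centres, the number contributing the first 80 subjects (Protocol B.1.2), it is about 3 × 10⁻²².

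**5. Ceiling on the likelihood-ratio statistic.** The interaction statistic cannot exceed the gain of the saturated model over a centre-only model. With equal arms within centre, that gain is at most 4·ln 2 = 2.77 per event. It is reached only if every subject in one arm of a centre has an MAE and none in the other arm does. The 0.15 critical value on 49 df is 59.2.

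- 21 events: 21 × 2.773 = 58.2 < 59.2, so significance is impossible.
- 22 events: 22 × 2.773 = 61.0, so significance is possible only in an extreme arrangement.
- 11 events: 30.5. This stays below the critical value down to 25 centres (31.1 on 24 df).

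**6. Simulation.** 433 subjects, 1,500 trials per scenario, denervation rate 3.5% unless stated. Wald rejected in 0% of trials and no finite maximum-likelihood estimate existed in any centre-model scenario.

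| Centres | Scenario | LR p<0.15, nominal df |
|---|---|---|
| 50 | no heterogeneity, control 0 to 7.1% | 0% (largest LR 46.6) |
| 50 | all denervation events in 5 centres, control 0 to 3.5% | 0% |
| 20 | no heterogeneity, control 0 to 7.1% | 0 to 3.9% |
| 20 | all denervation events in 5 centres, control 0 to 3.5% | 0 to 4.8% |
| 20 | denervation rate 7.1%, events in 5 centres, control 3.5% | 38% |

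If degrees of freedom are instead cut to centres with events, and control events are present, the LR test rejects in 36% to 72% of trials with no heterogeneity. That is far above the nominal 15%.

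**7. Regional models (9.3.2, 9.3.3).** These have four parameters. With two equal regions assumed, a finite estimate existed in 71% to 93% of simulated trials at control rates of 1.75% to 3.5%, and in 0% with no control events.

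**8. Estimand.** The SAP 9.9.1.1 hypothesis is the denervation rate below 7.1%. The SAP 9.3 interaction is whether the log odds ratio of denervation against control varies by centre or region. The odds ratio can be constant while the denervation rate differs between regions, and the reverse, so neither result answers the pooling question.

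**The case against.** Several points on the other side stand, and they limit the claim.

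- **Not every MAE model is unfittable.** A reader might carry the 100-parameter argument over to 9.3.2 and 9.3.3. Those models have four parameters and can often be fitted when both arms have events. Their defect is the wrong target.
- **Consistency is not automatic in every case.** A reader might infer that no data could ever contradict the rule. That is shown only for nominal degrees of freedom, about 50 centres and few events. The SAP fixes neither the test nor the degrees of freedom, and the 38% and 36% to 72% figures above show that other choices can reject.
- **Eleven is not a cap on the model's events.** It is the passing limit in the pooled denervation safety set. Control events would add to the model, and a failing safety result would exceed it.
- **Zero MAEs has not been established.** Protocol B.1.2 says "There were no major safety events reported at 1 month", among 331 randomised subjects. The MAE composite counts new renal artery stenosis to 6 months, and that report's category includes stroke, which is not an MAE component.
- **A between-arm MAE contrast does exist.** Protocol L.5 describes the composite as compared between groups, and SAP 5.2 and 9.9.2 compare it from 3 months. A treatment coefficient can be defined, but it is not the primary safety estimand.
- **The rule gates nothing.** The exact binomial test, its sample and its cut-off are the same whichever way 9.3 comes out.

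None of this rescues the step from a non-significant interaction to consistency of the primary safety endpoint.

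**Conclusion.** The point holds in a limited form. At about 50 centres the 9.3.1 MAE model has no finite estimates at the event counts the SAP expects, and an LR test on nominal degrees of freedom cannot reject with 21 or fewer MAEs in total. The resulting statements of consistency and poolability are uninformative there. With fewer centres, more events or reduced degrees of freedom the test is unreliable rather than certain to pass. Separately, all three MAE rules attribute the interaction to an endpoint that has no treatment contrast.

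The result rests on the 3.5% denervation rate, up to 50 centres, 1:1 allocation within centre and an assumed control rate of 0% to 7.1%. The number of centres that actually enrolled is not given.

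A reader might infer that the primary safety conclusion is undermined. The documents do not support that, because the performance-goal test does not depend on 9.3. The change is worth making because a stated rule yields an unsupported conclusion, but it does not affect the trial's success criteria.

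**What to change.** - Delete the treatment-by-centre MAE rule in SAP 9.3.1.
- In 9.3.1 to 9.3.3, delete the inference that a non-significant interaction shows consistency of the primary safety endpoint.
- Instead, report denervation-arm MAE counts with exact 95% confidence intervals by region and by source study (the SAP Table 2 sources).
- List MAEs by centre without centre-level intervals. At about four subjects per cell these say little: the exact upper limit for 0/4 is 1 − 0.025^(1/4) = 60%.
- Compare denervation-arm MAE rates between regions by an exact or Firth-penalised method only if events allow. State in advance that with zero or few events safety poolability is described and no homogeneity claim is made.
- Keep the blood-pressure interaction models for efficacy poolability only. Consistent blood-pressure effects do not show consistent safety.

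The cost is SAP wording, with little or no added analysis. The downside is that there is no longer a formal pass or fail statement on safety poolability.

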## 9.3.2. Poolability of US and Canada

The following analyses will be performed to evaluate the poolability of US and Canadian sites. If the resulting tests are significant at the 0.15 level, further exploratory analysis will be attempted to identify covariates that may explain differences. Otherwise, the data will be considered to be poolable between these regions.

- A logistic regression will be conducted, with MAE as the dependent variable, and treatment, US/Canada, treatment \* US/Canada as independent variables. If the interaction term is not significant at 0.15 level, then the treatment effect in the primary safety endpoint is considered consistent between US and Canadian regions.
- A linear regression will be conducted, with change in systolic blood pressure from baseline to 3 months as measured by 24-hour systolic Ambulatory Blood Pressure Monitoring (ABPM) as the dependent variable, and baseline systolic ABPM, treatment, US/Canada, treatment \* US/Canada as independent variables. If the interaction term is not significant at 0.15 level, then the treatment effect in the primary effectiveness endpoint is considered consistent between US and Canadian regions.

### 9.3.3. Poolability of North America (US and Canada)/Rest of World (ROW)

The following analyses will be performed to evaluate the poolability of data from North America (NA) and Rest of World (ROW) sites. If the resulting tests are significant at the 0.15 level, further exploratory analysis will be attempted to identify covariates that may explain differences. Otherwise, the data will be considered to be poolable across regions.

- A logistic regression will be conducted, with MAE as the dependent variable, and treatment, NA/ROW, treatment \* NA/ROW as independent variables. If the interaction term is not significant at 0.15 level, then the treatment effect in the primary safety endpoint is considered consistent between NA and ROW subgroups.
- A linear regression will be conducted, with change in systolic blood pressure from baseline to 3
  months as measured by 24-hour systolic Ambulatory Blood Pressure Monitoring (ABPM) as the
  dependent variable, and baseline systolic ABPM, treatment, NA/ROW, treatment \* NA/ROW as
  independent variables. If the interaction term is not significant at 0.15 level, then the treatment
  effect in the primary effectiveness endpoint is considered consistent between NA and ROW
  subgroups.

## 9.4. Handling of Missing Data and Dropouts

Every effort will be made to minimize missing data for the primary and secondary powered efficacy endpoints. A secondary analysis will be performed for both efficacy endpoints where missing outcome data are imputed using SAS PROC MI. Missing 3-month outcomes will be imputed using baseline SBP, treatment group, age, gender and BMI. One hundred imputed datasets will be generated, and a pooled estimate of the treatment effect will be generated using SAS PROC MIANALYZE.

